6.1.3. Electrocardiogram (ECG)

ECG will be performed at the screening visit (V1), at each subsequent visit from V2 to V8 for the double blind phase, and all visits of the open-label period, using the internationally recognized 12-lead ECG recording which includes date, time, initials of the technician/nurse, initials of the investigator or its deputy, at least 2 complexes for each lead and a single lead run. The corresponding source data will consist of the Cardiograph paper print-outs that should be kept in the file and a copy provided to Bioprojet. Main ECG parameters including heart rate, sinusal rhythm PR, QRS, and Fridericia's corrected QTc interval (QTcF = $QT/\sqrt[3]{(60/HR)}$) QTc interval will be analyzed and should be recorded.

All ECGs will be reviewed a posteriori by a central reviewer.

6.1.4. Blood Laboratory tests and Urinalysis

A full laboratory test should be performed at screening visit (V1), at the end of the double blind treatment (V7 or at early withdrawal visit), and at during open-label period at V10, V13, then every 6-month. All laboratory tests will be performed according to the Good Laboratory Practice by site-dependent Laboratory and tests data should be analyzed, reported and duly signed by its responsible. The results of laboratory tests as paper print outs should be reviewed and assessed (dated and signed) by the investigator at the next visit and reported in the specific form of the CRF.

The following blood parameters should be evaluated:

- Hematology: Red Blood Cell Count, White Blood Cell Count including differential (absolute value), Hemoglobin, Haematocrit, Mean corpuscular volume (MCV), Platelet Count (Absolute).
- Biochemistry Tests (Serum/plasma): Sodium (Na), Potassium (K), Chloride (Cl), Creatinine, Alkaline phosphatases, Urea, Alanine aminotransferase (ALAT), Aspartate aminotransferase (ASAT), Gamma-glutamyltranspeptidase (GGT), Total Bilirubin, Blood glucose, triglycerides, total cholesterol, Quick Time.
- β-hCG serum Pregnancy Test should be performed in all pubescent female patients with child-bearing potential. The absence of pregnancy should be confirmed before entering the study.

BIOPROJET Version 3.0 Protocol P11-06/ BF2.649 September 30th, 2020

EudraCT number: 2013-001506-29

All laboratory test results will be coded by using the 3 points scale as following:

- 0 =within the normal limits

- 1 = anomaly but no clinical significant

- 2 = anomaly clinically significant

Results of the clinical laboratory tests performed at screening will be included in the subject's

CRF and considered as baseline values before the product administration.

In addition a semi-quantitative ("dipstick") analysis for pH, ketone bodies, proteins, glucose

and blood should be evaluated. If any of these parameters gives a positive result, a quantitative

analysis will be performed to characterize or count: crystals, casts, epithelial cells, white blood

cells, red blood cells and bacteria if required by the investigator.

Follow-up of laboratory test abnormalities

The best interest of the subjects will always come before that of the trial. Abnormalities of any

laboratory tests considered to represent a significant danger to the subject will lead to immediate

discontinuation of the drug and the study monitor and Sponsor must be informed immediately.

In the event of abnormalities considered not to represent a danger, continuation of the drug will

be allowed after discussion with the study monitor. These subjects will be followed up with

appropriate medical management until they return to normal or baseline values or clinical

diagnostics of undercurrent illness is confirmed. The results of all known laboratory tests

required by the protocol will be held / recorded in the subject's CRFs. All clinically important

abnormal laboratory tests occurring during the study will be repeated at appropriate intervals

until they return to baseline or to a level deemed acceptable by the investigator and the study

monitor.

6.1.5.

Adverse Events

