3.7.2.4. Blood Laboratory tests, urinalysis, urinary drug testing

A full laboratory test should be performed at screening (V1), at the final double-blind treatment

phase evaluation visit (V7) and at early withdrawal visit and during the open-label period at

V10, V13 and all subsequent visits. Blood samples will be collected and all laboratory tests

will be performed according to the Good Laboratory Practice (OECD GLP Principles) by site-

dependent Laboratory. The results of laboratory tests will be interpreted by the investigator.

Laboratory abnormalities will be defined as laboratory test results that are outside the reference

range as defined by the normal range from the testing laboratory. Clinically significant

abnormal value at V1 will be determined by the investigator and will exclude patients from

study participation. The results of abnormal values of laboratory tests will be reported in the

CRF beside the normal range value given by the testing laboratory, the original document

containing all the tested values will be kept in the patient study file.

Blood laboratory test parameters and intra individual changes in these parameters will be

reported and analyzed in all patients.

- Hematology: Red Blood Cells, White Blood Cells (differential count, absolute value),

hemoglobin, haematocrit, Mean corpuscular volume (MCV), platelet count.

- Biochemistry: sodium, potassium, chloride, creatinine, alkaline phosphatases, urea,

alanineaminotransferase (ALAT), aspartate aminotransferase (ASAT), gamma glutamyl

BIOPROJET Version 3.0 Protocol P11-06/ BF2.649 September 30th, 2020

EudraCT number: 2013-001506-29

transpeptidase (GGT), total bilirubin, glucose, triglycerides, total cholesterol, quick time.

- Hormonology: βHCG (only for pubescent female).

- Urinalysis: semi-quantitative ("dipstick") analysis for pH, ketone bodies, proteins, glucose,

blood. If any of these parameters gives a positive result, a quantitative analysis will be

performed to characterize or count: crystals, casts, epithelial cells, white blood cells, red blood

cells and bacteria if required by the investigator.

- Urine drug testing: test of abuse of drugs will be performed on urine samples from 12 years.

Screened drugs are amphetamines, barbiturates, benzodiazepines, cannabinoids (THC) and

Opioids.

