BF2.649 at 5 mg/day: 1 tablet of BF2.649 5 mg or placebo in the morning during 7 days, or BF2.649 at 10 mg/day: 2 tablets of BF2.649 5 mg or placebo in the morning during 7 days, or BF2.649 at 20 mg/day: 1 tablet of BF2.649 20 mg or placebo in the morning during 7 days, or BF2.649 at 40 mg/day: 2 tablets of BF2.649 20 mg or placebo in the morning during 7 days. Treatment dosage at 40mg/day not allowed for patient with a weight less than 40 kg.

- -V5 (D28±2): No increase of BF2.649 dosage will be authorized, but it will be possible to decrease the dose, if the tolerance requires it. From this visit onwards, no dose change will be allowed.
- Week 5 to week 8: according to the investigator's prescription patients for whom the optimal dose level is estimated will continue at the same dose or the level dose will be reduced based on the tolerance to the product.

BF2.649 at 5 mg/day: 1 tablet of BF2.649 5 mg or placebo in the morning during 28 days, or BF2.649 at 10 mg/day: 2 tablets of BF2.649 5 mg or placebo in the morning during 28 days, or BF2.649 at 20 mg/day: 1 tablet of BF2.649 20 mg or placebo in the morning during 28 days, or BF2.649 at 40 mg/day: 2 tablets of BF2.649 20 mg or placebo in the morning during 28 days. Treatment dosage at 40mg/day not allowed for patient with a weight less than 40kg.

- V7 (D56± 2): Prescription of 1-week of placebo for all patients.

In open-label period patients will start pitolisant treatment with escalating doses scheme, as follows:

- V8 (D63 \pm 2)
- Week 10: BF2.649 at 5 mg/day: 1 tablet of BF2.649 5 mg in the morning during 7 days.
- Week 11: BF2.649 at 10 mg/day: 2 tablets of BF2.649 5 mg in the morning during 7 days.
 - $-V9 (D77\pm 2)$:
- Week 12: according to the investigator's prescription patients for whom the optimal dose level is estimated will continue at the same dose or if not sufficiently improved in their symptoms, and with a good tolerance, will increase to a higher dose or the level dose will be reduced based on the tolerance to the product.

BF2.649 at 5 mg/day: 1 tablet of BF2.649 5 mg in the morning during 7 days, or

EudraCT number: 2013-001506-29

BF2.649 at 10 mg/day: 2 tablets of BF2.649 5 mg in the morning during 7 days, or BF2.649 at 20 mg/day: 1 tablet of BF2.649 20 mg in the morning during 7 days, or

 $-V10 (D84\pm 2)$:

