- From Week 13: according to the investigator's prescription patients for whom the optimal dose level is estimated will continue at the same dose or if not sufficiently improved in their symptoms, and with a good tolerance, will increase to a higher dose or the level dose will be reduced based on the tolerance to the product.

BF2.649 at 5 mg/day: 1 tablet of BF2.649 5 mg in the morning during 28 days, or

BF2.649 at 10 mg/day: 2 tablets of BF2.649 5 mg in the morning during 28 days, or

BF2.649 at 15 mg/day: 3 tablets of BF2.649 5 mg in the morning during 28 days, or

BF2.649 at 20 mg/day: 1 tablet of BF2.649 20 mg in the morning during 28 days, or

BF2.649 at 30 mg/day: 2 tablets of BF2.649 5 mg and 1 tablet of BF2.649 20 mg in the morning during 28 days, or

BF2.649 at 40 mg/day: 2 tablets of BF2.649 20 mg or placebo in the morning during 28 days. Treatment dosage at 40mg/day not allowed for patient with a weight less than 40 kg.

At D91 during the phone contact the dose will be reduce in case of poor tolerance, when applicable.

$-V11 (D112\pm 2)$:

According to the investigator's prescription patients for whom the optimal dose level is estimated will continue at the same dose or if not sufficiently improved in their symptoms, and with a good tolerance, will increase to a higher dose or the level dose will be reduced based on the tolerance to the product.

BF2.649 at 5 mg/day: 1 tablet of BF2.649 5 mg in the morning during 3-month, or

BF2.649 at 10 mg/day: 2 tablets of BF2.649 5 mg in the morning during 3-month, or

BF2.649 at 15 mg/day: 3 tablets of BF2.649 5 mg in the morning during 3-month, or

BF2.649 at 20 mg/day: 1 tablet of BF2.649 20 mg in the morning during 3-month, or

BF2.649 at 30 mg/day: 2 tablets of BF2.649 5 mg and 1 tablet of BF2.649 20 mg in the morning during 3-month, or

BF2.649 at 40 mg/day: 2 tablets of BF2.649 20 mg or placebo in the morning during 3-month. Treatment dosage at 40mg/day not allowed for patient with a weight less than 40 kg.

 $-V12 (D196\pm 2)$:

According to the investigator's prescription patients for whom the optimal dose level is Confidential 68

estimated will continue at the same dose or if not sufficiently improved in their symptoms, and with a good tolerance, will increase to a higher dose or the level dose will be reduced based on the tolerance to the product.

BF2.649 at 5 mg/day: 1 tablet of BF2.649 5 mg in the morning during 6-month, or

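### Section 6.1.4 sets laboratory review for the next visit, which in the open-label phase allows about six months on pitolisant before a result is assessed

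*Protocol*

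**What the plan says.** Protocol section 6.1.4 gives the only timing instruction for the investigator's review of laboratory results. The print-outs "should be reviewed and assessed (dated and signed) by the investigator at the next visit and reported in the specific form of the CRF". Section 3.7.2.4 adds who does it but not when: "The results of laboratory tests will be interpreted by the investigator". SAP section 4.5.4.3 repeats that statement, also without a time.

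The follow-up paragraph of section 6.1.4 points towards prompt action. It opens with "The best interest of the subjects will always come before that of the trial". When an abnormality is judged a serious hazard for the child, the response is stated as "discontinuation of the drug and the study monitor and Sponsor must be informed immediately", and the stop itself is also to be immediate. For abnormalities judged not dangerous, treatment may go on once the matter has been discussed with the study monitor, and clinically important abnormal tests are to be repeated. The recording duty covers "The results of all known laboratory tests" that the protocol requires, with no deadline.

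Sections 3.7.2.4 and 6.1.4 place the samples at V1, V7 (or early withdrawal), V10, V13 and every six months after that. Sections 4.2, 5.2.13 and 5.2.16 dispense 28 days of drug at V10 and six months of drug at V13 and each later visit.

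**The concern.** A duty to stop immediately is only as fast as the assessment that triggers it, and the only stated time for that assessment is the next visit. Where visits are close together, or the child is not on active drug, this makes no difference. In the open-label phase the sampling visit is also the dispensing visit, so the child goes home with the full supply before the result is known.

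Transaminases, bilirubin, creatinine and, in pubescent girls, β-HCG are at stake. A site could comply with the sentence while an abnormal value from V13 or a later sample stays unassessed until the whole six-month supply has been taken.

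V13 carries particular weight. No laboratory sample is scheduled between V10 and V13. Open-label dosing is capped at 20 mg/day until V10, and 30 and 40 mg/day become available only from that visit. For a child who was randomized to placebo, V13 is therefore the first scheduled sample after any exposure above 20 mg/day.

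**Working it through.** **Inputs.** Visit days come from the synopsis, the two time-and-events schedules and sections 4.2 and 5.2: V1 D−14, V2 D0 ±2, V7 D56 ±2, V8 D63 ±2, V10 D84 ±2, V11 D112, V13 D364 ±7, then a visit every six months. Six months is taken as 182 days (364 / 2).

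**The plan's own figure.** V10 to V11 is 112 − 84 = 28 days, which matches the 28-day supply dispensed at V10.

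**Gap from each sample to the next visit.** Nominal gap = day of next visit − day of sample. Shortest gap = earliest next visit − latest sample. Longest gap = latest next visit − earliest sample.

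| Sample | Next visit | Nominal (days) | With windows (days) | Treatment in between |
|---|---|---|---|---|
| V1 | V2 | 0 − (−14) = 14 | 14 − 2 = 12 to 14 + 2 = 16 | none; before the first dose |
| V7 | V8 | 63 − 56 = 7 | 61 − 58 = 3 to 65 − 54 = 11 | placebo |
| V10 | V11 (±7) | 112 − 84 = 28 | 105 − 86 = 19 to 119 − 82 = 37 | daily pitolisant |
| V13 and later | six months on | 182 | 182 − 14 = 168 to 182 + 14 = 196 | daily pitolisant |

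- **V7.** Section 4.2 confirms the placebo week: "Prescription of 1-week of placebo for all patients".
- **V11 window.** The synopsis, the open-label schedule and section 5.2.14 give ±7 days. Section 4.2 gives ±2, which narrows the range after V10 to 110 − 86 = 24 up to 114 − 82 = 32 days.
- **Window after V13.** The protocol gives none for the later visits. The range 168 to 196 assumes that ±7 continues to apply.
- **Withdrawal samples.** The drug has already been stopped. The only gap is that no review date is set.

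**Contacts in between.** After V10 there is one telephone contact, T2. The synopsis and section 4.2 place it at D91 ("At D91 during the phone contact the dose will be reduce in case of poor tolerance, when applicable"); section 5.2.12 places it at D98. That is 91 − 84 = 7 days after V10 (90 − 86 = 4 to 92 − 82 = 10), or 98 − 84 = 14 days (97 − 86 = 11 to 99 − 82 = 17). T2 covers adverse events, efficacy, tolerance and dose. Laboratory review is not listed. From V13 onward no contact is scheduled between the six-monthly visits.

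**Order of events in the safety rules.** Each rule that could shorten the gap starts from a judgement on the result:

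- stopping the drug applies to an abnormality considered dangerous;
- discussion with the monitor applies to one considered not dangerous;
- repeat testing applies to one considered clinically important;
- recording a laboratory finding as an adverse event (section 6.1.5.1) applies to one considered clinically relevant.

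None of these brings the judgement itself forward.

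**The case against.** The best reply is that the sentence is about paperwork. It speaks of paper print-outs, a signature, a date and the CRF form, and it is worded as a recommendation. On that reading the next visit is when the file is completed, and the investigator would naturally have seen the report earlier. The rest of section 6.1.4 supports this: the duties to stop, to consult the monitor and to repeat tests make little sense if reports lie unread. There are other safeguards too. Serious adverse events must be reported within 24 hours, the investigator is to be reachable by telephone, and the trial runs under GCP with periodic monitoring. The timing suits V1 and V7 well, which suggests blinded-phase text carried over into the open-label phase.

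Much of this stands. Earlier review is not forbidden, the intent is clearly to act promptly, T2 offers a chance to raise a known result after V10, and the V1, V7 and withdrawal samples leave little or no exposure. What does not stand is the reading as a filing rule only. The sentence names review and assessment as well as signature and CRF entry, and sets all of them for the next visit. The other safeguards show what should follow an assessment, or give general oversight; none sets a date for it.

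**Conclusion.** The concern holds and should be fixed. Read literally, section 6.1.4 lets a laboratory result from V13 or any later sample go unassessed for about six months of daily pitolisant. After V10 the gap is smaller, 28 days, and is partly eased by T2.

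The intervals follow directly from the visit schedule. They rest on counting six months as 182 days and, for the range after V13, on the assumed ±7-day window. The finding is about what the wording allows; the documents show no delayed review at any site. The double-blind comparison and its endpoints are not affected, and the SAP covers only the blinded part.

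**What to change.** In section 6.1.4, replace the next-visit timing with a duty on receipt. Suggested wording: *The investigator reviews, signs and dates each laboratory report on receipt, including reports from premature-withdrawal samples. CRF entry may be completed at the next visit, or on receipt where no visit remains.*

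This lines up the timing instruction with the immediate-stop rule in the same section. It needs one sentence in an amendment, a reminder to sites and slightly prompter paperwork. No test, visit, stopping threshold or clinical criterion changes.

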6.1.5.1. Definitions

Period of observation

For the purpose of this study, the period of observation extends from the time the patient gives

informed consent (Visit 0) until one month after the last drug administration and until resolution

of ongoing drug related adverse event. Any adverse events observed by the investigator or

reported by the patient during the period of observation must be documented in the CRF.

Adverse event

The term **Adverse Event** covers any sign, symptom, syndrome, or illness which appears or

BIOPROJET Version 3.0
Protocol P11-06/ BF2.649 September 30th, 2020

EudraCT number: 2013-001506-29

worsens in a patient during the observation period in the clinical study, and which may impair

the patient's well-being.

The term also covers laboratory findings or results of other diagnostic procedures which are

considered to be clinically relevant (e.g., requiring unscheduled diagnostic procedures or

treatment measures, or result in withdrawal from the study).

An adverse event may be:

A new illness:

The worsening of a sign or symptom of the condition under treatment, or of a concomitant

illness;

An effect of the study medication;

A combination of two or more of these factors.

No causal relationship with the study medication or with the clinical study itself is implied by

the use of the term "Adverse Event."

• Exemption conditions

In this study in narcoleptic patients, symptoms like hallucinations, sleep attacks and sudden

onset of sleep should be considered as symptoms of the underlying condition and not as adverse

event, and should only be reported as Adverse Event in case of worsening or unusual form.

• Treatment-Emergent Adverse Event (TEAE)

A treatment-emergent adverse event is defined as any event not present prior to the initiation

of the study treatments, or any event already present which worsens either in intensity, or

frequency following the exposure to the study treatment.

• Adverse Drug Reaction (ADR)

All noxious and unintended responses to a medicinal product related to any dose should be

considered as an Adverse Drug Reaction. The responses to a medicinal product means that a

causal relationship between a medicinal product and an Adverse Event is at least a reasonable

possibility, i.e. the relationship cannot be ruled out. The causal relationship should be assessed

as defined below §7.2.5.3 (assessment of causality).

• Unexpected Adverse Drug Reaction

An Adverse Reaction, the nature or severity of which is not consistent with the applicable

BIOPROJET Version 3.0
Protocol P11-06/ BF2.649 September 30th, 2020

EudraCT number: 2013-001506-29

product information (e.g. Investigator Brochure).

• Serious Adverse Event (SAE) or Serious Adverse Drug Reaction (Serious ADR)

A Serious Adverse Event is one that at any dose:

- Results in death;
- Is life-threatening¹;
- Requires patient hospitalization or prolongation of existing hospitalization;
- Results in persistent or significant disability/incapacity²;
- Is a congenital anomaly/birth defect;
- Is medically important³.

1 "Life-threatening" means that the patient was at immediate risk of death at the time of the serious adverse event; it does not refer to a serious adverse event that hypothetically might have caused death if it were more severe.

2 "Persistent or significant disability or incapacity" means that there is a substantial disruption of a person's ability to carry out normal life functions.

³ Medical and scientific judgment should be exercised in deciding whether other adverse events may be considered serious because they jeopardize the patient, or may require intervention to prevent one of the other outcomes listed in the definition above. The List of Critical Terms (1998 adaptation of WHO Adverse Reaction Terminology Critical Terms List) should be used as guidance for adverse events that may be considered serious because they are medically important.

Cases involving cancer as an Adverse Event should be reported as "serious" using the criterion "medically important" if no other serious criterion is met.

Cases of overdose with an adverse event that meets one of the criteria given above should of course be reported as "serious". There is no antidote; in case of overdose, the patient has to be hospitalized in order to control his/her vital functions.

A serious adverse drug reaction is a serious adverse event which is related to the medicinal product whatever the dose.

• Clarification of the difference in meaning between "severe" and "serious"

The terms "severe" and "serious" are not synonymous:

- "severe" is used to **describe the intensity** (severity) of a specific event, which could be rated *mild*, *moderate or severe*. The event itself, however, may be of relatively

minor medical significance (such as severe headache).

- "serious" is **based on patient/event outcome** or action criteria usually associated with events that pose a threat to a patient's life or functioning. "Seriousness" (not severity) serves as a guide for defining regulatory reporting obligations.

6.1.5.2. *Monitoring and recording of adverse events*

The tolerance will be assessed by the occurrence of adverse and unexpected events, spontaneously reported by the patient or discovered during investigator's interview. The investigator or a designed member of his/her staff will probe each patient on any adverse experiences which may have occurred. The investigator should always ask the same question when conducting the verbal probe in order to ensure uniformity between patients. The investigator should ask:

- How are you doing (feeling)?

Based on the patient's response to this question, the investigator should ask additional questions relevant to the specific compliant such as:

- How severe is/was the symptom?
- How often did the symptom occur?
- How long did the symptom last?

For each unexpected or adverse effect, regardless the suspected causal relationship to study drug, the investigator have to report on the Adverse Event page(s) of the CRF the relevant information of AE including the nature, the anteriority (emergent or not), the timing of event occurrence and resolution, the frequency (intermittent or continuous), the severity, the seriousness (serious/non-serious), the relationship with the study compound, and actions taken to counteract the adverse experience. The investigator has also to pursue and obtain adequate information in order to determine the outcome of the adverse event and also to assess whether it meets the criteria for classification as a serious adverse event requiring immediate notification to the sponsor (see below). Follow-up of AEs is required until the event or its after-effects will be resolved or stabilized at an acceptable level with respect to the investigator opinion, even after the date of therapy discontinuation

